
2.1 Risk / Benefit Assessment

NA

3 STUDY OBJECTIVES

3.1 Primary Objective

To Investigate the effectiveness of seaweed (E. cava) in reducing postprandial blood glucose and plasma insulin level (to determine insulin sensitivity) in pre-diabetic patients, compared to placebo.

3.2 Secondary Objectives

Investigate the safeness and potential adverse effect of applying sea weed (E. cava) as a therapeutic diet composition on patient with pre-diabetes, compared to placebo.

4 STUDY DESIGN

4.1 Study Overview

This is a single center, double-blind, placebo-controlled, randomized study. 30 (number) of subjects are planned. Because the study only investigating the acute effect of the study interventional product, each subject will be administered a single dose of either study dietary supplement or placebo only one time. Subjects will be assigned to the treatments in random order. Evaluations will be taken at baseline and every 30 min following the ingestion of carbohydrates for the following 2 hours at the interval of 30, 60, 90, 120 min.

Screening data will be reviewed to determine subject eligibility. Subjects who meet all inclusion criteria and none of the exclusion criteria will be entered into the study.

The following treatment regimens will be used:

- A dietary supplement E.cava extracted capsule (seaweed) - at dose of 580 mg.
- Placebo (dextrin) – at a dose of 500 mg.

Total duration of subject participation will be six weeks. Total duration of the study is expected to be 12 weeks.

5 CRITERIA FOR EVALUATION

5.1 Primary Efficacy Endpoint

Reduction in postprandial blood glucose and insulin level compare to baseline.

As the dietary supplement (seaweed) is expected to have an effect on a-amylase and a-glucosidase enzymes that are responsible for breaking down carbohydrates which. Thus, postprandial blood glucose level and postprandial insulin level are best available way to see the effect of the product as it is expected to directly affect blood sugar enzymes that may lead to glycemic index control. As it is mentioned previously, this study is investigating the acute effect of the investigational product which will only compare change in PPBG and PPIL to baseline which will last only for one 3 hours in only one visit.

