10 EVALUATIONS BY VISIT

10.1 Visit 1 (Day1 /Week 1/Month 1)

1. Review the study with the subject (subject's legal representative) and obtain written informed consent.
2. Assign the subject a unique screening number.
3. Record demographics data.
4. Record medical history, including a history of pre-diabetic, diagnosis date.
5. Perform a complete physical examination.
6. Perform and record vital signs.
7. Perform and record results of blood pressure testing.
8. Collect blood for clinical laboratory tests (baseline of blood glucose level).
9. Schedule subject for Visit 2 in different days.
10. List all additional procedures, such as Randomize subject

10.2 Visit 2

1. Perform abbreviated physical examination.
2. Perform and record vital signs.
3. Collect blood for clinical laboratory tests (baseline of blood glucose and insulin levels).
4. Administer either study dietary supplement (seaweed) or placebo based on blinded randomization.
5. Perform carbohydrates ingestion
6. Collect blood for clinical laboratory tests (blood glucose and insulin levels 30 min after administration of study treatment).
7. Collect blood for clinical laboratory tests (blood glucose and insulin levels 60 min after administration of study treatment).
8. Collect blood for clinical laboratory tests (blood glucose and insulin levels 90 min after administration of study treatment).
9. Collect blood for clinical laboratory tests (blood glucose and insulin levels 120 min after administration of study treatment).

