14.3 Analysis of Primary Endpoint

Mean (standard deviation) will be reported for normally distributed data, whereas median (interquartile range) will be reported for not normally distributed data. Either independent t-test or Mann-Whitney test, based on normality of data, will be used to determine the difference between the two groups for both PPBG and PIL at a significant level of $p < 0.05$. Incremental area under the curve (iAUC), time to peak and peak blood concentration assessment will be used to assess postprandial responses of for plasma glucose and insulin level. Safety and tolerability data will be summarized by treatment group.

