APPENDIX 1.

	VISIT 1 (Day/Week/Month #) ^a	VISIT 2 (Day/Week/Month #) ^a
Informed Consent	X	
Medical History	X	
Complete Physical Exam	X	
Height	X	X
Weight	X	X
Vital Signs	X	X
Exercise Level	X	
Baseline Fasting Blood glucose Level	X	X
Postprandial Blood glucose Level		X
Baseline Insulin Level		X
Postprandial Insulin Level		X
ESR	X	
Randomization	X	
Dispensing or Administration of Study Drug		X

Concomitant Medication Review		X
Adverse Experiences		X

^a ±2 days

Required Components of Informed Consent

Informed consent is not a single event or just a form to be signed; it is an educational process that takes place between the investigator and the prospective subject. The basic elements of the consent process include:

full disclosure of the nature of the research and the participant's involvement, adequate comprehension on the part of the potential participant, and the participant's voluntary choice to participate.

It is the investigator's responsibility to document that the informed consent process has taken place, and an informed consent form is the standard for documenting the process for research projects involving human participants.

Consent forms must contain all the required components of informed consent as defined in SOP 9: Informed Consent Options, Processes, and Documentation and summarized below. The consent form must be written in language that is easy for a potential participant to understand and assures that individual's comprehension. Therefore, avoiding technical terms and complex sentences, even for the educated layperson, is very important.

When the participant population is not homogeneous, different consent documents may be required for different groups of people. If the research population will include participants under 18 years of age, then the IRB will expect investigators to use an assent form and a parental permission form instead (see SOP 11: Informed Consent, Enrollment, and Other Considerations for Research Involving Children). Similarly, research with cognitively or decisionally impaired individuals will require documented consent from another party—namely that person's legally authorized representative (see SOP 9, section 8 and/or SOP 10: xxx).

The IRB also recognizes that there are instances when documenting written informed consent is not appropriate to a research project. Alternatives to using a signed form for documenting informed consent are detailed in SOP 9.

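### Section 5.1 defines the primary endpoint as a reduction from a pre-carbohydrate baseline, which contradicts the placebo comparison in 3.1 and 14.3 and does not isolate the product effect

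*Combined protocol and SAP*

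**What the plan says.** **Endpoint.** Section 5.1 defines the primary efficacy endpoint as "Reduction in postprandial blood glucose and insulin level compare to baseline". It ends by describing a study "which will only compare change in PPBG and PPIL to baseline which will last only for one 3 hours in only one visit". The primary endpoint row of the synopsis does not help, because it lists only how glucose and insulin are assayed.

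**Baseline.** In section 10.2 (Visit 2), step 3 is "Collect blood for clinical laboratory tests (baseline of blood glucose and insulin levels", step 4 is the capsule and step 5 is "Perform carbohydrates ingestion". Appendix 1 calls the glucose baseline "Baseline Fasting Blood glucose Level" at both visits, and schedules postprandial glucose and insulin at Visit 2 only. Section 4.1 gives each subject a single dose.

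**Comparator elsewhere.** The objective in 3.1 concerns lowering both measures "in pre-diabetic patients, compared to placebo". In 14.3 an independent t-test or Mann-Whitney test "will be used to determine the difference between the two groups for both PPBG and PIL". Section 14.3 also names incremental area under the curve (iAUC), peak and time to peak as ways to assess the response. The sample size in 14.6 uses a two-group formula with a difference between means.

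**The concern.** The endpoint compares a value taken after a carbohydrate load with a value taken before it. No untreated challenge is scheduled, so no subject has a post-load value without the study capsule to serve as a reference. Any change from baseline within an arm is the sum of the load and the product effect, and the two cannot be separated without the other arm.

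The direction is also doubtful. Section 5.1 bases the expected benefit on enzymes that break down carbohydrate. That mechanism would blunt a rise; it gives no reason to expect values below fasting. The summaries in 14.3, such as peak and iAUC, likewise describe a rise.

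What is at stake is which result is reported as primary. Section 14 says that a detailed SAP is still to be written and may modify the analysis, so its author could take 5.1 as the definition and report within-arm change. The background (1.2 and 2) already shows this habit. It describes a 12-week trial whose insulin difference from placebo was not significant, then points to the significant within-group fall. In the present trial that kind of result would not answer the placebo-controlled objective.

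**Working it through.** **1. The plan's own figure.** Inputs from 14.6: SD = 32, d = 38, z-values 1.96 and 0.84.

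n = 2 × 32² × (1.96 + 0.84)² / 38² = 2 × 1024 × 7.84 / 1444 = 16056.32 / 1444 = 11.12, rounded up to 12 per group. The stated 12 is reproduced. The formula is for a difference between two groups, so the sample size supports 3.1 and 14.3 rather than 5.1.

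**2. The sections side by side.**

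| Section | What is compared | With what |
|---|---|---|
| 3.1 | postprandial glucose and insulin | placebo |
| 5.1 | postprandial glucose and insulin | baseline |
| 14.3 | PPBG and insulin | the other group |
| 14.6 | mean values | the other group |

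Section 5.1 is the exception. Its baseline can only be a pre-load value. The Visit 2 sample precedes capsule and carbohydrate, and the Visit 1 baseline in Appendix 1 is fasting glucose, with no insulin.

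**3. What a full planned benefit looks like under 5.1.** Assume that d = 38 is in mg/dL of post-load glucose and that the arms have equal baseline means. If placebo rises by R at a given time, then

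seaweed mean change from baseline = R − 38.

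The documents give neither R nor the amount of carbohydrate, so R is shown over an assumed range:

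| Assumed placebo rise R (mg/dL) | Seaweed mean change | Seaweed minus placebo |
|---|---|---|
| 20 | −18 | −38 |
| 30 | −8 | −38 |
| 38 | 0 | −38 |
| 50 | +12 | −38 |
| 60 | +22 | −38 |
| 80 | +42 | −38 |
| 100 | +62 | −38 |

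The benefit is 38 in every row. The change from baseline changes sign at R = 38 and depends on the load as much as on the product. The difference between arms is the only column that isolates the product. No such calculation is possible for insulin, because the documents give no planning difference for it.

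**4. Does the correction alter the sample size?** If SD 32 and d 38 apply to the measure tested, 12 per group stands. Power is then 83% at 12 and 90% at 15 per group (normal approximation), or 79% and 88% with the t distribution. The 15 per group is 30 subjects at 1:1 (4.1, 8.1).

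If SD 32 describes a single post-load value and the measure becomes change from baseline, then with equal variances and an assumed correlation ρ, SD of change = 32 × √(2(1 − ρ)):

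| ρ (assumed) | SD of change | n per group |
|---|---|---|
| 0.3 | 37.9 | 16 |
| 0.5 | 32.0 | 12 |
| 0.7 | 24.8 | 7 |

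At ρ = 0.3 the requirement slightly exceeds the 15 available. For iAUC these inputs do not carry over directly if they are concentrations, since iAUC is concentration multiplied by time.

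**The case against.** The strongest defence is that the trial as planned can still answer its question. Section 5.1 contains no success threshold and no test. The only primary test, in 14.3 and the synopsis, is between groups. No within-arm test is planned anywhere. This stands. A reader might infer from 5.1 that a working product would fail the trial; the documents do not support that, because the 14.3 test could detect a blunted rise.

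Secondly, the restrictive wording in 5.1 may only mean that the data are acute and come from one visit; 4.1 uses the word in that way. That is a fair reading, so the clause need not exclude placebo. It still names baseline as the sole reference, and nothing else in 5.1 names placebo.

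Thirdly, iAUC is ordinarily measured relative to baseline, so 5.1 and 14.3 read together could mean change from baseline compared between arms. This is plausible, but the plan does not say so and does not define iAUC.

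Finally, a reader might infer that glucose must stay above baseline in both arms throughout. The documents do not establish this. They give no post-load values, no carbohydrate amount and no units for d, and a late sample such as 120 min could approach or fall below fasting in some subjects. A fall of that kind could occur in both arms without any product effect, so it would not rescue the definition.

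**Conclusion.** The concern holds as a fault in the endpoint definition. Section 5.1 names a reference that cannot separate product from carbohydrate load, and it contradicts 3.1, 14.3 and the basis of 14.6. The planned between-group test is not at fault.

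On size: under the assumptions that d = 38 is mg/dL and that baseline means are equal, a full planned benefit appears as a mean fall from baseline only at times when the placebo rise is below 38 mg/dL, and as a rise whenever it is above. Which of these applies at each sample cannot be settled from the documents. The contradiction between sections, and the mixing of load and product effect, need none of these assumptions. For insulin, the word fasting is not written against the baseline, but the sample is drawn at the same pre-load step, so the reasoning is the same without a figure.

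**What to change.** 1. In 5.1, define the primary endpoint as the seaweed-placebo difference in the post-carbohydrate response. Use one named summary already in 14.3, for example iAUC from 0 to 120 min above the same-visit pre-load value, for glucose and for insulin.
2. In 14.3, make the primary test use that same measure, and state how iAUC is calculated, including the treatment of area below the pre-load value. The time origin must also be reconciled: 4.1 counts the samples from the carbohydrate and 10.2 from administration of the capsule.
3. In 5.1, delete "which will only compare change in PPBG and PPIL to baseline". The limitation to acute, single-visit data can stay.
4. State that within-arm change from baseline is descriptive and is not evidence of effect.
5. Make the synopsis endpoint row match.

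**Cost.** The definition needs text changes only; every sample required is already scheduled. The one substantive task is to confirm that SD 32 and d 38, with their units, apply to the chosen measure. If they do not, the power with 30 subjects must be restated.

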5.2 Secondary Efficacy Endpoints

In order to assess side effects of study intervention, measurement of side effects will be obtained by using an arbitrary scale, similar to that used by Paradis et al (12), that allow participants to rate symptoms of intolerance by indicating whether each side effect was absent (0), of mild intensity (1), of moderate intensity (2), or of severe intensity (3). The side effect questionnaire, will be required to be completed within 24 hours after intervention or placebo ingestion. The side effect will include headache, energy levels, appetite, gastrointestinal symptoms, unusual pain or sensations, cardiac palpitations, balance disorders, and anxiety.

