CONTROL PRODUCT, DOSE AND ROUTE OF ADMINISTRATION	Product plain dextrin as a placebo at 500 mg dose Product will be administered only one time at the only one visit to investigate the acute effect of the investigational product. administration will be orally.
DURATION OF SUBJECT PARTICIPATION AND DURATION OF STUDY	Subjects will be on study for only one time for only 3 hours Screening: one visit Treatment: one time at the only one visit. Follow-up: one day The total duration of the study is expected to be 4 months. 2 months for subject recruitment and 2 months for final subject follow-up as they will visit in different days.
CONCOMITANT MEDICATIONS	
 Allowed: 
 any medication that are not listed in prohibited list. Prohibited: 
 any treatment with either insulin or anti-diabetic drugs. any other natural health products known to impact blood sugar, or polyphenol absorption (e.g. fish oil). Any liver, thyroid, or gastrointestinal disorders medications.
EFFICACY EVALUATIONS	NA
PRIMARY ENDPOINT	
 Plasma glucose concentration will be determined immediately by blood finger-prick sample following standard procedure using Accu-Chek® aviva (Roche Diagnostics, Rotkreuz, Switzerland), Whereas, plasma insulin will be measured at the laboratory department at KKUH using enzyme-linked immunosorbent assay (ELISA)
SECONDARY ENDPOINTS	
 Participant/s will be asked to indicate whether side effects are absent, mild, moderate or severe by giving scores as 0,1,2,3, respectively. The side effect questionnaire, will be required to be completed within 24 hours after intervention or placebo ingestion.
OTHER EVALUATIONS	NA
SAFETY	Change in blood glucose level from baseline to more than 240 mg /dl or

EVALUATIONS
	
less than 70 mg /dl Adverse events such as: Headach, Bloating or Minor abdominal pain

PLANNED INTERIM ANALYSES
	
When approximately 50% of patients have completed the study through Visit 2, an interim analysis for safety will be conducted by an independent data monitoring committee. Serious adverse events will be monitored by the committee on an ongoing basis throughout the study.

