
(15). According to the knowledge of researcher, no study has reported any significant differences between brown algae and placebo in terms of measuring adverse effect (9-14). Lee et al, have reported similar incidence of adverse event between groups (22.2 vs 16.2) for brown algae group compared to placebo, respectively (11). Similarly, paradis et al, find that 13 subjects in each group have reported adverse effect with minimal intensity (1 in a scale of 0 to 3) being the most reported for most of measured symptoms (12).

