14.4 Analysis of Secondary Endpoints

Mann-Whitney test will be used to determine differences for symptoms of intolerance between groups.

Adverse events will be tabulated by treatment group and will include the number of patients for whom the event occurred, the rate of occurrence, and the severity and relationship to study drug.

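### The side-effect form has a 24-hour deadline but no fixed window and no pre-dose rating, so the only tested tolerability measure loses sensitivity

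*Combined protocol and SAP*

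**What the plan says.** Section 5.2 has each subject rate side effects as "absent (0), of mild intensity (1), of moderate intensity (2), or of severe intensity (3"). The items are "headache, energy levels, appetite, gastrointestinal symptoms, unusual pain or sensations, cardiac palpitations, balance disorders, and anxiety". On timing it says only "The side effect questionnaire, will be required to be completed within 24 hours after intervention or placebo ingestion". The synopsis repeats this, again as "required to be completed within 24 hours after intervention or placebo ingestion", and separately gives one day of follow-up.

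Section 10.2 lists the Visit 2 procedures. Before the capsule these are an abbreviated physical examination, vital signs and blood: "Collect blood for clinical laboratory tests (baseline of blood glucose and insulin levels"). The last step is the sample for "blood glucose and insulin levels 120 min after administration of study treatment". The questionnaire does not appear, before or after dosing. Appendix 1 has no row for it either; it marks adverse experiences at Visit 2 only.

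Section 14.4 then states: "Mann-Whitney test will be used to determine differences for symptoms of intolerance between groups". It mentions no pre-dose reference. Adverse events are tabulated by group, and no test is planned for them or for the glucose limits in section 5.3. The questionnaire is therefore the only safety or tolerability measure with a planned test, and it serves the only secondary objective (section 3.2).

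**The concern.** There are two gaps.

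- **Window.** A form filled in at the 120-minute sample and one filled in at hour 24 both comply. The first covers about 2 hours and the second up to 24. A symptom that starts after an early completion is not scored.
- **Baseline.** Headache, energy, appetite and anxiety can be present before the capsule, in people who arrive fasting and are about to have repeated blood samples. Energy and appetite are also states rather than symptoms, and a rating from absent to severe is hard to interpret without a reference point.

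The stake is how a null result will be read. Missed late symptoms and added background symptoms both dilute a true difference between the arms. For a safety objective that is the unhelpful direction, because no difference becomes easy to reach and says little. A pre-dose rating cannot be recovered after dosing.

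**Working it through.** **Plan's own figure.** The documents give no symptom rate, onset time or power for this questionnaire. The one sample-size figure concerns a difference in means and reproduces: 2 × 32² × 2.8² / 38² = 16056.32 / 1444 = 11.12, rounded up to 12 per group. It does not bear on the symptom scores. Section 8.1 randomizes up to 30 subjects 1:1, so 15 per arm is used below.

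**Share of onsets captured.** Let completion time t be spread evenly over 2 to 24 hours (an assumption).

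- Onset uniform over 24 h: capture is t/24. At t = 3 this is 3/24 = 12.5%. The mean t is 13, so the average is 13/24 = 54%.
- Onset uniform over 6 h: capture is t/6 up to 6 h and 1 afterwards. At t = 3 this is 50%. The average is (4 × 0.667 + 18)/22 = 94%.

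With an assumed 30% incidence of an item, 15 × 0.30 = 4.5 cases are expected per arm. Of these, 4.5 × 0.54 = 2.4 are scored in the first case and 4.5 × 0.94 = 4.2 in the second.

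**Effect on the test.** The planned Mann-Whitney test was simulated for one item with 15 per arm and 4000 runs per setting. All rates are assumptions: new symptoms by 24 h in 5% on placebo and 45% on active, scored 1 to 3; pre-existing symptoms scored 1 to 2, equally common in both arms and persisting; onset uniform over 24 h. Power at the 5% level:

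| Pre-existing | Variable time, raw score (as planned) | Variable time, pre-dose score subtracted | Fixed 24 h, raw score | Fixed 24 h, pre-dose score subtracted |
|---|---|---|---|---|
| 0% | 38% | 38% | 77% | 77% |
| 10% | 23% | 34% | 59% | 74% |
| 20% | 19% | 32% | 47% | 71% |
| 30% | 15% | 28% | 39% | 66% |

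With no product effect (5% in both arms), the planned test rejected in 0.1%, 2.9%, 4.9% and 4.4% of runs at the same four rates, so never above 5%. At 20% pre-existing symptoms both arms showed 22% with a symptom, although only 5% had a new one. With the effect present, the observed rates were 39.6% and 22.1%.

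**Sensitivity to onset.** With onset uniform over 6 h and no pre-existing symptoms, power was 74% with variable completion and 76% with fixed completion. With 24 h onset, the same runs gave 36% and 77%.

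**Which score to test.** If pre-dose symptoms persist, a simple change score and an increase floored at zero are identical, because the post-dose score cannot be lower than the pre-dose score. They differ once pre-dose symptoms resolve. In separate runs with a fixed window and 20% pre-existing symptoms:

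| Pre-dose symptoms | Raw | Simple change | Increase, floored at 0 |
|---|---|---|---|
| Persist | 41% | 67% | about 66% |
| Half persist | 55% | 52% | about 66% |
| Resolve | 76% | 43% | about 66% |

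The two sets of runs differ by a few points at the same setting (47% and 71% against 41% and 67%), so only the pattern should be relied on.

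**The case against.** A reader might infer that existing symptoms will be counted as product effects in the tested comparison. The documents do not support that. Allocation is 1:1 and random (section 8.1), the study is double-blind (section 8.2), and the test is between groups, so existing symptoms and completion times fall alike in both arms on average. The stronger reading is true only of each arm's rates read on their own.

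The size can also be overstated. Nothing in the documents supports uniform onset over 24 hours, and a single dose studied for its acute effect may well act early. With 6-hour onset, most of the window loss disappears. This stands, and the 54% figure is one end of a range.

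Nor does section 1.2 show that background symptoms are common. It reports that "13 subjects in each group have reported adverse effect with minimal intensity", without a denominator, and these were adverse effects during treatment or placebo, not symptoms before dosing.

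Sections 9.1.6 and 11.1 collect adverse events throughout the study with start and stop times, which could date a symptom missed by an early form or present beforehand. This helps in part. However, section 11.1 ties the questioning to visits, Appendix 1 marks Visit 2 only, and the result is tabulated, not tested.

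Finally, one day of follow-up may mean that a 24-hour observation period was intended. No passage fixes it, and that reading would not supply the missing pre-dose rating.

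**Conclusion.** The concern holds as a loss of sensitivity and of interpretability, not as bias in the comparison. Following the plan exactly allows 2-hour and 24-hour forms in the same test and leaves no way to separate new symptoms from existing ones. The test's false-positive rate is not inflated.

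Under the assumed rates with 24-hour onset, power is 15% to 38% as planned and 66% to 77% with both gaps closed. If onset is within about 6 hours, the unequal windows cost little (74% against 76%). The missing baseline alone still costs power where pre-dose symptoms persist: 47% against 71% at a 20% pre-existing rate and a fixed window. Where they resolve before the post-dose rating, it costs no power, though nobody could tell from the data which case applied. All of these rates are assumptions, so the direction is firmer than the size.

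The primary glucose and insulin analyses are unaffected. A non-significant symptom test from the current plan should not be presented as evidence that the product is tolerated as well as placebo.

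**What to change.** - **Section 5.2, synopsis, section 10.2 and Appendix 1:** have each subject complete the same form twice, once at Visit 2 before the capsule and once at 24 hours after ingestion, the second covering the whole 24 hours. Record the completion time. State how the second form is returned, for example taken home or completed by telephone, since no visit is scheduled then.
- **Section 14.4:** keep the Mann-Whitney test, but apply it to treatment-emergent severity: the increase where the post-dose score exceeds the pre-dose score, and 0 otherwise. Do not use a simple change score, which loses power when pre-dose symptoms resolve. Report raw post-dose scores alongside, because they are more sensitive in that case.

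The cost is one extra completion of a short form at a visit already planned, plus wording in these places. The downsides are some reliance on 24-hour recall and a few late or missing 24-hour forms. The change has to be made before dosing starts.

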8 STUDY TREATMENTS

8.1 Method of Assigning Subjects to Treatment Groups

Up to 30 eligible patients will be randomly assigned to the dietary supplement seaweed or placebo treatment groups in a 1:1 ratio using a SAS-based computer-generated randomization scheme developed by a study investigator who will not be involved in data collection and analysis. Participants and other investigators will be blinded to which supplement is consumed each testing occasion for each participant until data analysis completed. At screening visit investigators will complete patient required data as detailed in the Study Manual, and fax it to the investigator who is responsible for randomization. The investigator who responsible for randomization will send back participants data encoded with numbers and supplements (intervention & placebo) with letters (A, B). Study intervention or placebo will be encapsulated in identical capsules and will be labelled with the letter A and B to conceal which supplement is given to each participants.

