14.6 Sample Size and Randomization

Sample size was calculated based in similar study (24) using sample size determination equation:

$$\frac{2SD^2(Z_{\alpha/2} + Z_B)^2}{d^2}$$

$$n = 2(32)^2(1.96+0.84)^2 / 38^2 = 2(1024) (2.8)^2 / 1444 = 2048*7.84 / 1444$$

$$= 16056.32 / 1444$$

$$= 11.11 \approx 12 \text{ subjects/group}$$

whereas:

- $Z_{\alpha/2}$ = standard normal variate for level of significant, at 5% type 1 error, (if $p < 0.05 = 1.96$).
- Z_B = Standard normal variate for power (for 80% power = 0.84, for 90% power = 1.28).
- SD= Standard Deviation (determined from the literature).
- d= effect size – difference between mean values (determined from the literature).

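### Two of the eight side-effect items, energy and appetite, are scored 0 to 3 without a direction and without a pre-dose rating, so their scores cannot show which way either one moved (minor)

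*Combined protocol and SAP*

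**What the plan says.** Section 5.2 describes a participant-rated questionnaire for symptoms of intolerance, due within 24 hours after the capsule. The participant scores the items by "indicating whether each side effect was absent (0), of mild intensity (1), of moderate intensity (2), or of severe intensity (3"). The items are: "The side effect will include headache, energy levels, appetite, gastrointestinal symptoms, unusual pain or sensations, cardiac palpitations, balance disorders, and anxiety".

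The Secondary Endpoints row of the Protocol Synopsis gives the same anchors, asking participants to "indicate whether side effects are absent, mild, moderate or severe by giving scores as 0,1,2,3, respectively". It lists no items and gives no direction.

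Section 14.4 gives the analysis in one sentence: "Mann-Whitney test will be used to determine differences for symptoms of intolerance between groups". It does not say whether items are tested singly or as a total. The synopsis has the same test.

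Section 5.3 names headache, bloating and minor abdominal pain as adverse events and does not define the energy or appetite items. Neither Section 10.2 (Visit 2) nor the schedule in Appendix 1 includes a symptom rating before the capsule, although Appendix 1 has a fasting glucose at that visit.

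**The concern.** An absent-to-severe scale suits an item that names a complaint, because more of it is worse and none of it is 0. Energy and appetite can each rise or fall, and the scale has no sign and no increase or decrease option. A participant who lost appetite and one who gained it, to the same degree, would be recorded identically. The documents also do not say whether a gain in energy should be scored as intolerance at all.

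The form is filled in only after ingestion, by people who come to Visit 2 fasting. Tiredness or hunger present before the capsule cannot be told apart from an effect of it.

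At stake is the interpretation of the only stated secondary endpoint, which serves the only secondary objective (safety compared with placebo). Direction cannot be recovered from unsigned scores after the data are collected, so the wording has to be settled before enrolment.

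**Working it through.** **Inputs**
- Items: 8 (Section 5.2). Six name a complaint: headache, gastrointestinal symptoms, pain or sensations, palpitations, balance disorders and anxiety. Two do not: energy and appetite. 2/8 = 25%.
- Scale: 0, 1, 2, 3, unsigned (Section 5.2 and Protocol Synopsis).
- Test: Mann-Whitney between groups (Section 14.4).
- Size: "Up to 30 eligible patients will be randomly assigned to the dietary supplement seaweed or placebo treatment groups in a 1:1 ratio" (Section 8.1), so 30/2 = 15 per arm.
- Score distributions: none in the documents. Those below are assumptions.

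**The plan's own figure.** The only computed design figure is the sample size in Section 14.6: 2 × 32² × 2.8² / 38² = 16056.32 / 1444 = 11.12, rounded up to 12 per group. It reproduces. It concerns a difference in means and does not depend on the questionnaire, so nothing here changes it.

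**Step 1: what an unsigned score loses.** Suppose 5 of 15 active participants lose appetite by one grade, 5 of 15 placebo participants gain appetite by one grade, and the rest do not change.
- Scored as written, each arm has ten 0s and five 1s. U = 15 × 15 / 2 = 112.5, its null value, and p = 1.
- Scored with a sign (−1 for loss, +1 for gain), the active arm's only credit comes from ties at 0: U = 10 × 10 × 0.5 = 50 out of 225, p about 0.002 (normal approximation, tie and continuity corrections).
- Scored as two items, the reduced-appetite item has five 1s in the active arm and none on placebo: U = 5 × 15 + 0.5 × 10 × 15 = 150. The tie-corrected variance is (225/12) × [31 − (25³ − 25 + 5³ − 5)/(30 × 29)] = 242.5, so SD = 15.57. With the continuity correction z = (150 − 112.5 − 0.5)/15.57 = 2.38, p about 0.017. The increased-appetite item mirrors it. Direction is now visible.

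**Step 2: the same point by simulation.** Setting: 15 per arm, 4,000 runs for each row, every change in one arm a loss and every change in the other a gain, with equal intensity distributions. The table gives the share of runs with p < 0.05.

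| Assumed shares at intensity 0/1/2/3 | Unsigned score | Signed score |
|---|---|---|
| 0.4/0.3/0.2/0.1 | 5.0% | 100% |
| 0.6/0.2/0.15/0.05 | 4.65% | 99.9% |
| 0.3/0.3/0.25/0.15 | 4.45% | 100% |

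The unsigned score rejects at about its nominal 5% level against a complete reversal. This shows the mechanism only. Nothing in the documents suggests that such a reversal is likely.

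**Step 3: the missing pre-dose rating.** If the recorded score is the pre-existing level plus any change due to the capsule, the pre-existing part has the same expectation in both arms under randomisation. It widens the spread without shifting the expected difference. The documents give no figure from which to size this noise.

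**The case against.** The strongest reply is that the scale works for its purpose. Section 5.2 asks whether each side effect is absent, so a higher score means a more intense complaint whichever way appetite or energy moved. A higher distribution in the active arm would mean more symptom burden, and the secondary objective is safety, not the direction of appetite. That stands as far as it goes: burden is measured, and direction is not.

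It also disposes of several stronger readings that a reader might infer:
- *Someone with no energy scores 0, the best value.* What is absent at 0 is the side effect, not the energy. Taking the word literally is a risk of misreading on the form, not the evident intent.
- *The Mann-Whitney test is invalid here.* It compares ordered scores and has no built-in clinical direction. The limit lies in what the score means.
- *The tolerability conclusion rests on this form alone.* Adverse events are captured throughout (Section 9.1.6), asked about at each visit (Section 11.1), graded (Section 11.1.1) and tabulated by group (Section 14.4). Fatigue or loss of appetite reported there can be recorded as the named event.
- *Fasting symptoms bias the comparison.* Under double-blind randomisation they add noise. Carbohydrate is given at the same visit and the form may be filled in up to 24 hours later, so they need not dominate.

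Two further replies have force. The numerical examples are constructed. And Section 5.2 may only summarise a form that words these items better: it calls the scale similar to that of a cited crossover trial, and neither form is in the documents. If the actual form is already directional, copying its wording into Section 5.2 closes that part of the point.

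**Conclusion.** The point holds, at minor severity. As specified, 2 of the 8 items have no direction. On the natural reading, their scores show how much participants were troubled but not which way energy or appetite moved, and opposite shifts of equal intensity in the two arms cannot be detected. The absence of a pre-dose rating adds noise of unknown size to a comparison of about 15 per arm.

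This limits the questionnaire endpoint only. The other six items, the separate adverse-event tabulation, the sample size and the primary analysis are unaffected. The conclusion assumes that the form follows the item names in Section 5.2 and that the planned 30 are randomised 1:1. The documents do not support a claim that the questionnaire as a whole is uninterpretable or that the safety comparison is biased.

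**What to change.** Before enrolment:
1. In Section 5.2 and on the form, replace the energy item with reduced energy/fatigue, and split the appetite item into reduced appetite and increased appetite. Score each 0 to 3, with 0 meaning no such symptom. This makes 8 + 1 = 9 items.
2. Have participants complete the same form once before the capsule at Visit 2, and add this to Section 10.2 and Appendix 1.
3. In Section 14.4, state that the change from the pre-dose score is compared between groups, item by item, by Mann-Whitney.

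The cost is an edit to a questionnaire and about 2 minutes per participant at a visit already planned. Two small downsides: the items no longer match the cited trial's scale exactly, and a rise in energy is no longer an item of its own. No change is needed to the sample size or the primary analysis.
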